1.1 OBJECTIVES AND ENDPOINTS

Table 1 Objectives and Corresponding Endpoints

Primary Objective	Corresponding Endpoint

 To evaluate the antiviral activity of AT-527 compared with placebo 	
 Change from baseline in amount of SARS-CoV-2 virus RNA as measured by RT-PCR at specified timepoints
Secondary Objectives	Corresponding Endpoints

 To evaluate the antiviral activity of AT-527 compared with placebo 	
 Time to cessation of SARS-CoV-2 viral shedding as measured by RT-PCR Time to sustained non-detectable SARS-CoV-2 virus RNA Proportion of patients positive for SARS-CoV-2 virus RNA by RT-PCR at specified timepoints Area under the curve in the amount of SARS-CoV-2 virus RNA as measured by RT-PCR

 To evaluate the safety of AT-527 compared with placebo 	
 Incidence and severity of adverse events, with severity determined according to NCI CTCAE v5.0 Change from baseline in targeted vital signs, including SpO₂ Change from baseline in targeted clinical laboratory test results

 To characterize the PK profile of AT-511 (free base form of AT-527) and its major metabolites 	
 Plasma concentration of AT-511, AT-551, AT-229, and AT-273 (surrogate for the intracellular concentration of the active triphosphate metabolite AT-9010) at specified timepoints

 To evaluate the efficacy of AT-527 compared with placebo 	
 Time to alleviation or improvement of COVID-19 symptoms (Items 1-12 of the COVID-19 symptom diary) maintained for a duration of 21.5 hours, defined as follows: 
 For new symptoms: time from start of treatment to the alleviation of COVID-19 symptoms (i.e., a score of 0 [none] or 1 [mild] on the COVID-19 Symptom Diary) For pre-existing symptoms: time from start of treatment to when a patient's symptoms have been maintained or improved (note: improved requires at least a single category improvement from baseline on the Likert scale.) Time to alleviation or improvement of COVID-19 symptoms (Items 1-12 of the COVID-19 Symptom Diary) maintained for a duration of 43 hours, defined as follows: 
 For new symptoms: time from start of treatment to the alleviation of COVID-19 symptoms (i.e., a score of 0 [none] or 1 [mild] on the COVID-19 Symptom Diary) For pre-existing symptoms: time from start of treatment to when a patient's symptoms have been maintained or improved (note: improved requires at least a single

Table 1 Objectives and Corresponding Endpoints (cont.)

Secondary Objectives	Corresponding Endpoints

To evaluate the efficacy of AT-527 compared with placebo (contd..)	
category improvement from baseline on the Likert scale.)Time to alleviation of COVID-19 symptoms, defined as the length of time taken from start of treatment to the point at which the following criterion is met and maintained for at least 21.5 hours: Score of 0 or 1 on Items 1-12 of the COVID-19 Symptom Diary (without consideration for presence of pre-existing symptoms)Time to alleviation of COVID-19 symptoms, defined as the length of time taken from start of treatment to the point at which the following criterion is met and maintained for at least 43 hours: Score of 0 or 1 on Items 1-12 of the COVID-19 Symptom Diary (without consideration for presence of pre-existing symptoms)Duration of fever, defined as the time to return to an afebrile state (temperature $\leq 37.5^{\circ}\text{C}$) maintained for at least 21.5 hoursFrequency of COVID-19-related complications (death, hospitalization, radiologically confirmed pneumonia, acute respiratory failure, sepsis, coagulopathy, pericarditis, myocarditis, cardiac failure)Time to alleviation of an individual symptom, defined as the time taken from the start of treatment to the point at which the following criterion is met and maintained (for each individual symptom) for at least 21.5 hours:
Score of 0 or 1 for Items 1-12 of the COVID-19 Symptom DiaryScore of 0 for Items 13 and 14 of the COVID-19 Symptom Diary
Exploratory Objectives	Corresponding Endpoints

To evaluate the antiviral activity of AT-527 compared with placeboTo evaluate the relationship between drug exposure and antiviral activity of AT-527	
Treatment-emergent amino acid substitutions in SARS-CoV-2 viral genes (nsp12 and potentially other genes)Anti-SARS-CoV-2 antibody status/titer at specified timepointsChange from baseline in SARS-CoV-2 virus titer at specified timepointsTime to cessation of SARS-CoV-2 viral shedding as measured by virus titerProportion of patients with positive SARS-CoV-2 virus titer at specified timepointsArea under the curve of SARS-CoV-2 virus titerDrug susceptibility in patients with evaluable virus at specified timepoints 
Relationship between plasma concentration of AT-273 and anti-viral activity

Table 1 Objectives and Corresponding Endpoints (cont.)

Exploratory Objectives	Corresponding Endpoints

• To evaluate patient-reported COVID-19 symptom severity• To identify and/or evaluate biomarkers that are predictive of response to AT-527 (i.e., predictive biomarkers), are early surrogates of efficacy, are associated with progression to a more severe disease state (i.e., prognostic biomarkers), can provide evidence of AT-527 activity (i.e., pharmacodynamic biomarkers), or can increase the knowledge and understanding of disease biology and drug safety	
• Patient's global impression of severity of COVID-19 symptoms as assessed through the use of PGIS at Day 14 and Day 28• Relationship between biomarkers in blood, saliva, nasopharyngeal swab, and nasosorption samples (listed in Section 4.5.5 of the study protocol) and efficacy, safety, PK, or other biomarker endpoints

COVID-19=coronavirus disease 2019; NCI CTCAE=National Cancer Institute Common Terminology Criteria for Adverse Events; nsp12=non-structural protein 12; PGIS=Patient Global Impression of Severity; PK=pharmacokinetic; RT-PCR=reverse-transcription polymerase chain reaction; SARS-CoV-2=severe acute respiratory syndrome coronavirus-2; SpO₂=peripheral capillary oxygen saturation.

1.2 STUDY DESIGN

This is a Phase II, randomized, double-blind, placebo-controlled study to evaluate the antiviral activity, safety, pharmacokinetics, and efficacy of selected dose regimens of AT-527 compared with placebo in non-hospitalized adult patients with mild or moderate COVID-19. If all potential cohorts are fully enrolled, the study will enroll up to approximately 220 patients at approximately 52 sites globally.

Patients will be screened up to 72 hours prior to randomization. Patients who do not meet the criteria for participation in this study (screen failure) cannot be re-screened. The investigator will record reasons for screen failure in the screening log.

Eligible patients will be enrolled sequentially into one of up to five possible treatment cohorts (Cohorts A–E). Sixty patients will be enrolled into Cohort A; Cohorts B–E will enroll 40 patients each. Patients who withdraw from the study or who discontinue study treatment will not be replaced. However, patients who withdraw from the study after screening, but before receiving the first dose, will be replaced. However, they may not receive the same treatment as the patient they are replacing.

In Cohort A, patients will be randomized in a 1:1 ratio to receive either AT-527 550 mg tablets (or placebo) twice a day (BID) on Days 1–5, with assessment visits on Days 3, 5,

and 7. After 30 patients (50% enrolment) in Cohort A have completed assessments through Day 10, an interim review of safety data will be conducted to determine the AT-527 dose and regimen for Cohort B.

In Cohorts B–E, patients will be randomized in a 3:1 ratio to receive either AT-527 or placebo on Days 1 – 5, with assessment visits on Days 3, 5 and 7. Dose regimen decisions for Cohorts C–E will be made by the Sponsor study team following unblinded review of safety data by an Internal Monitoring Committee (IMC) after 20 patients (approximately 15 active and 5 placebo) enrolled in the previous cohort have completed assessments through Day 10. The maximum dose to be tested in the study will not exceed AT-527 1100 mg BID for 5 days. Depending on emerging data, the Sponsor may also evaluate regimens with doses of AT-527 lower than 550 mg BID. Cohorts evaluating such lower doses may be initiated at any time following the Cohort A interim safety review and will not require IMC oversight.

[figure not shown]
For all cohorts, visits may be conducted in clinic or by mobile nursing. Where local policies and local site logistics permit, patients may also be confined in clinic during Days 1 – 7. Where treatment occurs in the inpatient setting, the purpose of hospitalization must not be for severe COVID-19 requiring inpatient treatment. A safety follow-up telephone call will be conducted on Day 14 and an end of study safety follow-up telephone call on Day 33. The total study duration for each patient will be 33 days.

For all cohorts, a selection of different samples will be collected to assess SARS-CoV-2 viral status at various timepoints. To evaluate the PK properties of AT-527, PK samples will be collected at various timepoints. Patients will be closely monitored for COVID-19 signs and symptoms and adverse events (AEs); AEs will be graded according to National Cancer Institute Common Terminology Criteria for Adverse Events (NCI CTCAE) v5.0.

During Cohorts B–E, an IMC will provide additional safety oversight for cohorts evaluating regimens with AT-527 doses higher than 550 mg BID (refer to Section 1.2.2 for details).

The study schema is shown in [Figure 1](#).

Figure 1 Study Schema

BID = twice a day; COVID-19 = coronavirus disease 2019; IA = Interim Analysis; IMC = Internal Monitoring Committee; PBO = placebo; PO = orally; R = randomization; SARS-CoV-2 = severe acute respiratory syndrome coronavirus-2.

Note: Patients in Cohort A will be randomized in a 1:1 ratio (AT-527: placebo). Subsequent cohorts will be randomized in a 3:1 ratio (AT-527: placebo).

- ^a Planned interim safety analysis after the first 30 patients enrolled have completed assessments through Day 10 will inform dose regimen decision for Cohort B.
- ^b If a dose lower than 550 mg BID is evaluated in any of Cohorts B–E, no IMC input is required, and the cohort may be initiated at any time after the Cohort A interim safety analysis.
- ^c For cohorts evaluating regimens with AT-527 doses higher than 550 mg BID, the IMC will review unblinded safety data through Day 10 for the first 20 patients in the cohort. Dose regimen decisions for the next cohort will be made by the Sponsor study team following IMC review.

1.2.1 Treatment Assignment and Blinding

This is a randomized, double-blind study. After initial written or electronic informed consent has been obtained, all screening procedures and assessments have been completed, and eligibility has been established for a patient, the study site will obtain the patient's identification number and treatment assignment from an interactive voice or web-based response system (IxRS).

In Cohort A, patients will be randomly assigned to receive AT-527 or placebo in a 1:1 ratio. In subsequent cohorts, patients will be randomized to receive AT-527 or placebo in a 3:1 ratio. A permuted-block randomization method will be utilized to ensure a balanced assignment to each treatment group.

Study site personnel and patients will be blinded to treatment assignment during the study. Following interim analyses, the Sponsor study team and appropriate senior management personnel will be unblinded at a treatment group level; however, the Sponsor and its agents will be blinded to individual treatment assignment, with the exception of individuals who require access to patient treatment assignments to fulfill

their job roles during a clinical trial. These roles include the unblinding group responsible, clinical supply chain managers, sample handling staff, operational assay group personnel, IxRS service provider, and IMC members. Supporting biometrics staff (independent of the project team) will have access to the unblinded data to allow for data transfer, unblinding, and summarizing of safety data for IMC review.

While PK samples must be collected from patients assigned to the placebo group to maintain the blinding of treatment assignment, PK assay results for these patients are generally not needed for the safe conduct or proper interpretation of the study data. Laboratories responsible for performing study drug PK assays will be unblinded to patient treatment assignments to identify appropriate samples for analysis. PK samples from patients assigned to the placebo group will not be analyzed for study drug PK concentration except by request (e.g., to evaluate a possible error in dosing).

If unblinding is necessary for a medical emergency (e.g., in the case of a serious adverse event (SAE) for which patient management might be affected by knowledge of treatment assignment), the investigator will be able to break the treatment code by contacting the IxRS. The treatment code should not be broken except in emergency situations. The investigator is not required to contact the Medical Monitor prior to breaking the treatment code. However, the investigator should contact the Medical Monitor to discuss emergency unblinding after the treatment code has been broken.

If the investigator wishes to know the identity of the study drug for any reason other than a medical emergency, he or she should contact the Medical Monitor directly. The investigator should document and provide an explanation for any non-emergency unblinding. If the Medical Monitor agrees to patient unblinding, the investigator will be able to break the treatment code by contacting the IxRS.

As per health authority reporting requirements, the Sponsor's Drug Safety representative will break the treatment code for all serious, unexpected suspected adverse reactions that are considered by the investigator or Sponsor to be related to an investigational medicinal product (IMP). The patient may continue to receive treatment, and the investigator, patient, and Sponsor personnel, with the exception of the Drug Safety representative and personnel who must have access to patient treatment assignments to fulfill their roles (as defined above), will remain blinded to treatment assignment.

1.2.2 Data Monitoring

During Cohorts B–E, an IMC will provide additional safety oversight for cohorts evaluating regimens with AT-527 doses higher than 550 mg BID. The IMC will include representatives from Clinical Science and Clinical Safety who are independent of the Sponsor study team, and a Biostatistician who does not have regular contact with the sites. In addition to the ongoing assessment of the incidence, nature, and severity of AEs, SAEs, deaths, and vital signs and laboratory abnormalities performed by the

Medical Monitor, the IMC will review safety data through Day 10 for the first 20 patients enrolled in those cohorts.

The IMC will pause further enrollment in the study to conduct a comprehensive safety assessment of all cumulative data if any of the following criteria are met:

- Death in any patient for which the cause of death is judged by the investigator to have a reasonable possibility of relatedness to the study drug
- Occurrence in any patient of a life-threatening SAE for which the causal relationship is judged by the investigator to have a reasonable possibility of relatedness to the study drug
- Greater than 20% of the enrolled patients in any cohort experience clinically significant Grade 3 or 4 AEs judged by the investigator to have a reasonable possibility of relatedness to the study drug

The IMC will make recommendations as to the further conduct of the study as outlined in the IMC Charter. Other specific operational details such as the IMC's composition, frequency and timing of meetings, and members' roles and responsibilities will be detailed in the IMC Charter. Cohorts evaluating regimens with AT-527 doses lower than 550 mg BID will not require additional IMC oversight.

2. STATISTICAL HYPOTHESES

The primary virology analysis for this trial will evaluate the antiviral activity of AT-527 compared with placebo at Days 3, 5, and 7 to demonstrate superiority of AT-527 over placebo.

The following null and alternative hypothesis will be tested at a one-sided 0.10 significance level (equivalent to a two-sided 0.20 significance level):

$$H_0: CFB_{AT-527} \leq CFB_{Placebo} \quad \text{versus} \quad H_a: CFB_{AT-527} > CFB_{Placebo},$$

for which the CFB_{AT-527} and $CFB_{Placebo}$ refer to the decrease from baseline in amount of SARS-CoV-2 virus RNA as measured by reverse-transcription polymerase chain reaction (RT-PCR) for AT-527 and placebo at specified timepoints, respectively.

No alpha adjustments for multiple comparisons are planned.

3. SAMPLE SIZE DETERMINATION

The primary objective of this study is to evaluate the antiviral activity of AT-527 compared with placebo. Approximately 60 patients will be randomized in a 1:1 ratio in Cohort A to receive AT-527 or placebo. Each additional cohort will enroll approximately 40 patients in a 3:1 ratio to receive AT-527 or placebo, respectively.

The sample size is based on the primary endpoint of change from baseline in SARS-CoV-2 virus RNA measured by RT-PCR at a single timepoint. A sample size of

27 patients per treatment group (active or placebo) in the modified intent-to-treat infected (mITTi; defined in [Table 2](#)) population will result in at least 80% power to detect a mean reduction in change from baseline of between 0.7 and 1.1 log₁₀ copies using a two-sample t-test for comparison of means, assuming a standard deviation of between 1.2 and 1.85 (Regeneron 2020) and based on a 1-sided 10% alpha. The sample size has been adjusted to 30 patients per treatment group to account for an estimated 90% SARS-CoV-2 positive rate and is based on a single-cohort comparison of AT-527 versus placebo.

4. ANALYSIS SETS

Disposition summaries will be based on the intent-to-treat (ITT) population. All randomized patients will be included in the ITT population, and data will be summarized according to the randomized treatment assignment.

All primary and secondary virology and efficacy outcomes will be analyzed in the mITTi population. The mITTi population is defined as all patients randomized in the study who received any amount of study drug and had at least one positive SARS-CoV-2 RT-PCR test result above or equal to the limit of quantification (LOQ) during the study, with patients grouped according to the treatment assignment at randomization.

Safety analyses will be performed on the safety evaluable population, which consists of all patients who receive any amount of study drug. In all safety analyses, patients will be grouped according to the treatment that the patients actually received rather than the treatment assigned at randomization. Patients who received any dose of AT-527 will be summarized in the AT-527 group.

Pharmacokinetic analyses will be performed on the PK analysis population, which will consist of all patients in the ITT population who had at least one post-dose drug concentration measurement at a scheduled visit timepoint.

The analysis populations are defined in [Table 2](#).

Table 2 Analysis Sets

Population	Definition
ITT	All randomized patients, whether or not the patient received the assigned treatment.
Safety-evaluable	All patients who received at least one dose of study treatment.
mITTi	All patients randomized in the study that received any amount of study drug and had at least one positive central SARS-CoV-2 RT-PCR test result above or equal to the LOQ (by nasopharyngeal swab) during the study, with patients grouped according to the treatment assignment at randomization
PK population	All patients in the ITT population who had at least one post-dose drug concentration measurement at a scheduled visit timepoint

ITT=intent-to-treat; mITTi=modified intent-to-treat infected; LOQ=limit of quantification; PK=pharmacokinetic; RT-PCR=reverse-transcription polymerase chain reaction; SARS-CoV-2= severe acute respiratory syndrome coronavirus-2.

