6. STATISTICAL CONSIDERATIONS AND ANALYSIS PLAN

All primary and secondary virology and efficacy outcomes will be analyzed in the modified intent-to-treat infected (mITTi) population. The mITTi population is defined as all patients randomized in the study who received any amount of study drug and had at least one positive SARS-CoV-2 RT-PCR test result *above or equal to the limit of quantification (LOQ)* during the study, with patients grouped according to the treatment assignment at randomization.

Safety analyses will be performed on the safety evaluable population, which consists of all patients who receive any amount of study drug. In all safety analyses, patients will be grouped according to the treatment that the patients actually received rather than the treatment assigned at randomization.

For *Cohorts A–D*, the primary virology analysis will be performed as part of a Day 10 review (accompanied with key safety review if deemed necessary, further details will be included in the SAP) which is to be completed after all patients enrolled in the current cohort have completed assessments through Day 10. Other endpoints will be analyzed at the completion of each full cohort or at the completion of the study.

For *Cohorts A–D*, all analyses at the Day 10 review or at the completion of each cohort will compare each AT-527 dose group and a combined placebo group, including all placebo patients enrolled across cohorts up to the cohort being analyzed, while analyses performed at the completion of the study will compare each AT-527 dose group and a combined placebo group from *Cohorts A–D*.

For *Cohort E*, the primary virology analysis will be performed as part of a Day 14 review (accompanied with key safety review if deemed necessary, further details will be included in the SAP) which is to be completed after all patients in *Cohort E* have completed assessments through Day 14. Other endpoints will be analyzed at the completion of the cohort.

For *Cohort E*, all analyses will compare the AT-527 dose group and the placebo group from *Cohort E* only. Data from cohorts with the same dose may be pooled to further evaluate the primary endpoint as part of a sensitivity analysis. Full details of all planned tables, listings, graphs, and statistical methods will be provided in a Statistical Analysis Plan (SAP), which will be finalized prior to the end of the study.

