5. STATISTICAL ANALYSES

5.1 GENERAL CONSIDERATION

All virology and efficacy analyses will be performed on the mITTi population.

All primary and secondary virology endpoints will be produced using the nasopharyngeal swab samples. Additional descriptive analyses for saliva and serum samples will be performed on an exploratory basis for the primary and secondary virology endpoints, as required. A summary of the sampling differences between cohorts is provided in [Table 3](#). Refer to Appendix 1 and Appendix 2 of the study protocol for further details.

No alpha adjustments for multiple comparisons are planned.

For all cohorts, the primary virology analysis will be performed as part of a Day 10 Review (accompanied with key safety review if deemed necessary, see [Section 5.7.1](#)) which is to be completed after all patients enrolled in the current cohort have completed assessments through Day 10. Other endpoints will be analyzed at the completion of each full cohort or at the completion of the study. All analyses at the Day 10 review or at the completion of each cohort will compare each AT-527 dose group and a combined placebo group, including all placebo patients enrolled across cohorts up to the cohort being analyzed, while analyses performed at the completion of the study will compare each AT-527 dose group and a combined placebo group from all cohorts.

Table 3 Differences in Virology Sampling Between Cohorts

Assessment	Cohort A	Cohorts B–E
Nasopharyngeal swab sample for COVID-19 virology	Once a day on Days 1, 3, 5, and 7	Once a day on Days 1, 3, 5, and 7
Saliva sample for COVID-19 virology	NA	Once a day on Days 1, 3, 5, and 7
Serum sample for anti-SARS-CoV-2 antibodies and viral RNA	Once a day on Days 1 and 7	Once a day on Days 1, 3, 5, and 7

COVID-19 = coronavirus disease 2019; NA = not applicable; SARS-CoV-2 = severe acute respiratory syndrome coronavirus-2.

For virology endpoints, the time windows for each assessment are given in [Table 4](#). The time windows will be used for all virology endpoints except the time-to-event endpoints.

Table 4 Virology Assessment Time Windows

Scheduled Timepoint ^{a, b, d}	Acceptable Time Window
Baseline (Day 1 pre-dose)	Day 1 pre-dose ^c
Day 3	Day 2 – Day 3
Day 5	Day 4 – Day 5
Day 7	Day 6 – Day 8

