5.3.2 Main Analytical Approach for Primary Virology Endpoint

The primary virology endpoint analyses will be performed on the mITTi population using the nasopharyngeal swab data.

For each cohort, the change from baseline in the amount of SARS-CoV-2 virus RNA will be compared between the AT-527 group and the pooled placebo group (meaning all placebo patients up to and including the cohort being analyzed will be used to form the placebo comparator group) at Days 3, 5, and 7 using analysis of covariance (ANCOVA) with baseline viral load as a covariate.

The least squares mean (LSM) change and its standard error (SE) of means in each group, the difference between two groups in LSM change, SE, and 80% CI, and p-values will be presented. The LSM change will be presented graphically over time.

Additionally, descriptive summaries for the change from baseline will also be presented by treatment group. The change from baseline and the amount of SARS-CoV-2 virus RNA will also be presented graphically over time.

Baseline is defined as the Day 1 (pre-dose) nasopharyngeal swab ([Table 4](#)).

If the data are not normally distributed, a non-parametric alternative method will be used (e.g., Mann-Whitney U test) to compare distributions.

The qualitative result of the SARS-CoV-2 RT-PCR test is determined using cycle threshold (Ct) values. If the qualitative result is positive, then an associated quantitative result is also provided. The quantitative result is either numerical or below the limit of quantification (BLQ). The limit of quantification (LOQ) for the virus RNA is 120 copies/ml. If the virus RNA sample has a positive qualitative result, but a quantitative result BLQ, virus RNA will be imputed as LOQ – 1 (119 copies/mL). Negative qualitative samples will be imputed as LOQ/2 (60 copies/ml) before being transformed to the log10 scale. Samples reported as positive, but not quantifiable, will contribute to qualitative summaries, but will be treated as missing (not imputed) for quantitative summaries.

Missing data will not be imputed. Any missing data will not be included in the analyses.

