5.4.2 Secondary Endpoints

5.4.2.1 Secondary Endpoints (Virology)

All secondary virology analyses will be performed on the mITTi population.

All virology analyses will be performed using the nasopharyngeal swab data.

Descriptive analyses of saliva and serum samples will be performed on an exploratory basis for the primary and secondary virology endpoints, as required.

Time to event virology secondary endpoints

For time to event virology secondary endpoints, time will be calculated in hours.

- **Time to cessation of SARS-CoV-2 viral shedding as measured by RT-PCR**
 - Time to cessation of viral shedding by RT-PCR, in hours, is defined as the time between the initiation of any study treatment and first time when a negative or BLQ test result by RT-PCR is obtained. Patients who do not receive a negative or BLQ test result by RT-PCR by the last observation timepoint will be treated as censored at the final timepoint on Day 7.
- **Time to sustained non-detectable SARS-CoV-2 virus RNA**
 - Time to sustained non-detectable SARS-CoV-2 virus RNA, in hours, is defined as the time between the initiation of any study treatment and first time when a negative or BLQ test result by RT-PCR is obtained after which no positive test above or equal to the LOQ was reported. Patients who do not meet this endpoint by the last observation timepoint will be treated as censored at the final timepoint on Day 7.

These time-to-event endpoints will be summarized using descriptive statistics by treatment, as well as Kaplan-Meier plots. The median time to response from the Kaplan-Meier plots will be presented along with the 80% CI. If required, a hazard ratio may be produced adjusting for baseline viral load using a Cox proportional hazards model.

For all cohorts, the virology time-to-event endpoints will be described for the AT-527 group and the pooled placebo group through Day 7 using the mITTi population.

For virology time to event endpoints, deaths will be right censored at Day 7. Consequently, for these endpoints, participants censored on the final day reflect two different states, death or failure to meet the improvement outcome criterion. Therefore, it is important to understand the outcome in the context of the number and timing of deaths by treatment group.

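### The primary virology set can be entered through a post-dose swab, so for patients below LOQ at baseline membership depends on the measurements being analysed, and such patients have almost no viral load left to lose

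*SAP*

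**What the plan says.** SAP Section 4 defines mITTi as randomized patients who took any study drug and who "had at least one positive SARS-CoV-2 RT-PCR test result above or equal to the limit of quantification (LOQ) during the study". Table 2 in the same section is tighter about the sample: the patient must have "had at least one positive central SARS-CoV-2 RT-PCR test result above or equal to the LOQ (by nasopharyngeal swab) during the study". Protocol Section 6 uses the general form ("had at least one positive SARS-CoV-2 RT-PCR test result", at or above LOQ, at any time in the study), without the words central or nasopharyngeal. None of the three ties the qualifying result to baseline.

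The set carries the primary analysis: "The primary virology endpoint analyses will be performed on the mITTi population using the nasopharyngeal swab data". SAP Table 3 schedules the nasopharyngeal swabs "Once a day on Days 1, 3, 5, and 7"; Protocol Section 6.4.1 adds Day 14 for Cohort E. Days 3, 5 and 7 are also the primary-endpoint visits.

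SAP Section 5.3.2 states: "Baseline is defined as the Day 1 (pre-dose) nasopharyngeal swab". It also states: "Negative qualitative samples will be imputed as LOQ/2 (60 copies/ml) before being transformed to the log10 scale". A positive result below quantification becomes 119 copies/mL, and the LOQ is 120. In SAP Section 5.4.2.1, shedding ends at the "first time when a negative or BLQ test result by RT-PCR is obtained", counted from the start of treatment, with no requirement that the patient was positive beforehand.

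**The concern.** Take two patients who are both negative on the Day 1 central swab. One reaches LOQ on Day 5 and is analysed; the other stays below LOQ and is left out. What separates them is a post-randomization measurement that the drug is meant to influence. If AT-527 prevents conversion to quantifiable virus, it removes some of its own successes from the treated group.

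Those who do enter contribute little to a reduction endpoint. They start at or near the imputation floor and can only stay there or rise, which adds scatter around the treatment difference. In the shedding endpoint, a patient negative on Days 1 and 3 and at or above LOQ on Day 5 counts as having ceased on Day 3, before any quantifiable result.

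No listed analysis would show the effect. The sensitivity analyses in SAP Section 5.3.3 concern nominal sampling days and the all-cohort placebo group. The optional baseline viral-load subgroup in SAP Section 5.3.5 gives a median split as its example, which does not isolate these patients.

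**Working it through.** **1. The plan's sample sizes reproduce.** They come from Protocol Section 6.1 and SAP Section 3. Cohort E figures are from the Protocol only, because the SAP still describes Cohort E as 40 patients randomized 3:1. For a two-sample t-test the noncentrality is δ / (SD × √(2/n)).
- Cohorts A–D: δ 0.7, SD 1.2, n 27, one-sided 10%: power 80.1%. With δ 1.1 and SD 1.85: 81.2%. 27/0.9 = 30.
- Cohort E: δ 0.5, SD 1.25, n 100, one-sided 2.5%: noncentrality 0.5/(1.25 × √0.02) = 2.83, power 80.4%. 100/0.9 rounds up to 112.

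These figures are not in error. The point concerns who is counted.

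**2. What the imputation rule allows.** On the log10 scale, 60 is 1.778, 119 is 2.076 and 120 is 2.079.
- Negative baseline: change at the qualifying visit is at least log10(120/60) = +0.301. The largest fall at any visit is 0.
- Baseline below quantification: change at the qualifying visit is at least log10(120/119) = +0.004. The largest fall at any visit is log10(119/60) = 0.297.
- Design effects for comparison: 0.7–1.1 log10 (Cohorts A–D) and 0.5 (Cohort E).

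**3. Keeping or removing these patients.** Let f be the share of mITTi below LOQ at baseline. The documents do not give f; 2–10% is assumed. Removing them leaves n(1 − f) per arm with effect δ. Keeping them, if they show no treatment effect and the SD is unchanged, leaves n per arm with effect δ(1 − f).

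| f | A–D (0.7/1.2): remove | A–D: keep | Cohort E: remove | Cohort E: keep |
|---|---|---|---|---|
| 2% | 79.5% | 78.9% | 79.6% | 78.8% |
| 5% | 78.5% | 77.0% | 78.3% | 76.2% |
| 10% | 76.8% | 73.6% | 76.1% | 71.7% |

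For Cohort E at f = 10%, the noncentrality is 0.5/(1.25 × √(2/90)) = 2.68 if they are removed and 0.45/(1.25 × √0.02) = 2.55 if they are kept.

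**4. Simulation of Cohort E.** Assumptions: 112 per arm; 2–10% of randomized patients negative at baseline; half of those later at or above LOQ (at 10%, 112 × 0.10 × 0.5 = 5.6 per arm); ANCOVA on baseline. The loss is measured against the baseline-positive set.
- No drug effect of any kind: estimate about 0.00, one-sided rejection 2.3–2.8%, which is nominal.
- True effect 0.5, equal conversion: power loss from under 1 to about 14 points, depending on the baseline-negative share and the converters' viral load. At a 10% share, two separate runs gave 78% falling to 66% and 76.5% falling to 70.4%, with standard errors rising from 0.162 to 0.178 and from 0.161 to 0.172. One setting with converters averaging 5 log10 lost about 16 points, so the range is not a bound.
- Conversion 50% on placebo and 25% on AT-527, no effect in baseline-positive patients: the estimate moves by about 0.04–0.06 log10 in the drug's favour.

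**The case against.** The strongest reply is that few patients are affected. Everyone at or above LOQ on Day 1 is in the set regardless. Entry requires a positive local test, with screening no more than 72 hours before randomization, and symptom onset within 5 days. Baseline is an ANCOVA covariate, the study is declared hypothesis-generating, and Protocol Section 6.4 leaves room for sensitivity analyses. The paired endpoint of sustained non-detectability does not share the early-cessation artefact, because a later result at or above LOQ cancels the earlier negative one. All of this stands and limits the size. It does not remove the dependence on post-dose results, and the covariate reduces the problem without eliminating it.

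A reader might infer that the rule inflates type I error, since with 50% against 25% conversion and no effect in baseline-positive patients one simulation rejected in 4.5% of trials against a nominal 2.5%. That inference fails: a drug that halves conversion to quantifiable virus has an antiviral effect, so those rejections are not false positives.

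A reader might also take 10% as the documents' own baseline-negative share. The 90% positive rate in the sample-size sections is used to get from mITTi to randomized numbers. It describes patients outside the set, not patients inside it who were negative at baseline.

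Finally, mITTi also serves the symptom, fever and complication endpoints, which need no baseline viral load. The argument for restricting the set does not reach those.

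**Conclusion.** The point holds as a matter of definition. For patients without quantifiable virus on the Day 1 central swab, membership of the primary virology set is decided by the outcome measurements, and a negative baseline rules out any recorded fall. Under a complete null, with conversion also unaffected, the rule causes neither bias nor error inflation. Otherwise it costs precision, and the estimate shifts if the drug changes conversion.

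The size is uncertain. Both the baseline-negative share and the converters' viral load are assumptions, so the simulated power loss (under 1 to about 14 points for Cohort E) and the shift (about 0.04–0.06 log10) are illustrations. A single figure such as a fall from 78% to 66% should not be read as what the plan will lose. The documents support a worthwhile tightening of the virology set, not a conclusion that the primary analysis is invalid.

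**What to change.** In SAP Section 4 and Table 2, and in Protocol Section 6, define the set for the primary and secondary virology endpoints as randomized, dosed patients whose baseline central nasopharyngeal swab (baseline as in SAP Table 4) is at or above LOQ. Keep the current any-positive set as a named sensitivity analysis for those endpoints. Leave the symptom and complication endpoints on the current mITTi. Bring the SAP Section 4 sentence and the Protocol wording into line with Table 2 by specifying a central result from a nasopharyngeal swab; read alone, they could let a local screening RT-PCR qualify a patient.

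The cost is wording plus a few patients leaving the virology set. If f is 2%, 5% or 10%, the planned 27 per arm becomes 26.5, 25.6 or 24.3, and the planned 100 becomes 98, 95 or 90. Holding the planned numbers would take 31, 32 or 34 randomized per arm instead of 30, and 114, 117 or 124 instead of 112, from n/(0.9 × (1 − f)) rounded up. Even without that increase, the restricted set had the higher power in every row of the table and never cost power against the current set in the simulations.
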